9. SECONDARY ENDPOINTS

9.1 Acceptability

To assess acceptability of the study gel, we will focus on the ease of use and comfortability of the study product, as reported by participants, using information from the Exit Behavioral Survey. We will present results from the section B of the survey on Gel Acceptability, specifically the following two questions:

B1. Overall how easy or difficult was it to use the gel?

1. Very difficult
2. Difficult
3. Easy
4. Very easy

B2. Overall, how did it feel to have the gel inside you?

1. Very comfortable
2. Comfortable
3. Uncomfortable
4. Very uncomfortable

Results will be presented overall and by arm, with the number and percentage of participants in each category. To conduct formal statistical testing, collapsed categories will be created. For question B1, we will calculate the proportion of participants that responded “Easy” or “Very easy”. For question B2, we will calculate the proportion of participants that responded “Liked” or “Liked very much”. We will present the binomial proportions with exact 95% confidence intervals, overall and for each arm. Fisher’s Exact test will be used to test for differences between arms

Results will also be presented overall and by site, with no formal statistical testing.

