2.1 General Design Considerations

The following is a protocol summary of the study.

Protocol title:	A Randomized, Double Blind, Placebo-Controlled Phase 1 Safety and Pharmacokinetic Study of the Dapivirine Gel (0.05%) Administered Rectally to HIV-1 Seronegative Adults
Short Title:	Dapivirine Gel Rectal Safety and PK Study
Clinical Phase:	Phase 1
IND Sponsor:	DAIDS
Protocol Chair:	[name], FRCP
Sample Size:	approximately 27 participants
Study Population:	HIV-uninfected men and women between the ages of 18 and 45 years (inclusive)
Study Sites:	Sites selected by the MTN leadership
Study Design:	Phase 1, two-arm, placebo-controlled, double-blinded, multi-site, randomized trial (2:1)
Study Duration:	Approximately 40 days of follow-up per participant is planned with a projected accrual period of 6-8 months
Study Products:	Dapivirine gel (0.05%)

Study Regimen: Universal HEC placebo gel
Participants will be randomized in a 2:1 ratio to receive a single dose of either dapivirine gel or universal HEC placebo gel rectally, followed by 7 daily doses of the same product to be administered under direct observation in the clinic.

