2.2 Study Objectives and Endpoints

Primary Objectives:

Safety

- To assess the safety of dapivirine gel formulation when applied rectally.

Pharmacokinetics

- To characterize the systemic and compartmental pharmacokinetics of dapivirine gel following rectal application.

Secondary Objectives:

Acceptability

- To identify product attributes considered likely to challenge and facilitate future sustained use of rectally applied dapivirine gel.

Mucosal Safety

- To evaluate the mucosal safety of dapivirine gel when applied rectally.

Exploratory Objectives:

Ex Vivo Efficacy

- To assess the preliminary (ex vivo) efficacy of dapivirine gel formulation after product is applied rectally.

Pharmacokinetics

- To characterize the vaginal pharmacokinetics of dapivirine gel following rectal application in women.

Primary Endpoints:

Safety

- The proportion of participants with:
 - Grade 2 or higher AEs as defined by the Division of AIDS Table for Grading the Severity of Adult and Pediatric Adverse Events, Corrected Version 2.1, July 2017 and/or Addenda 1, 2 and 3 (Female Genital [Dated November 2007], Male Genital [Dated November 2007] and Rectal [Clarification Dated May 2012] Grading Tables for Use in Microbicide Studies).

Pharmacokinetics

- Dapivirine concentrations
 - Blood
 - Rectal fluid
 - Rectal mucosal tissue homogenates.

Secondary Endpoints:

Acceptability

- Product attributes considered likely challenge future sustained use

Mucosal Safety

- Rectal Proteomics
- Rectal transcriptome
- Rectal microflora
- Rectal histology
- Rectal tissue flow cytometry

Exploratory Endpoints:

Ex Vivo Efficacy

- Changes in HIV-1 p24 levels in colorectal explant culture supernatant
- Anti-HIV activity in rectal fluid
- Anti-HIV activity in cervicovaginal fluid (in women)

Pharmacokinetics

- Dapivirine concentrations
 - Cervicovaginal fluid (in women)
 - Cervical tissue (in women)

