6.1.5 Visit Adherence: Completion of Procedures

Visit adherence will be summarized by completion of required and expected procedures overall and by site. This will be done for the following procedures (we mark with asterisk (*) those procedures that are expected only for female participants): 1) Physical exam; 2) vital signs; 3) sexual lubricant form; 4) pregnancy tests *; 5) chemistries; 6) pelvic exam *; 7) rectal exam; 8) plasma archive; 9) plasma for PK; 10) HIV Test; 11) CVL for PD*; 12) cervicovaginal fluid for PK *; 13) cervical tissue for PK *; 14) rectal fluid for PK; 15) rectal tissue for PK; 16) rectal fluid for mucosal safety; 17) rectal tissue for mucosal safety; 18) rectal tissue for PD; 19) rectal enema effluent for PK/PD; 20) behavioral assessment; 21) In-depth interview. Tables displaying the number and percentages of participant-visits for each of these categories by arm and site will be presented. No formal statistical testing will be conducted.

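### Section 9.1 analyses two overall ratings, ease and comfort, and so does not by itself deliver an acceptability endpoint defined by product attributes and future use

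*SAP*

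**What the plan says.** Section 2.2 gives the acceptability objective as "To identify product attributes considered likely to challenge and facilitate future sustained use of rectally applied dapivirine gel" and the matching secondary endpoint as "Product attributes considered likely challenge future sustained use". The objective covers both hindrances and helps; the endpoint line names only the hindrances.

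Section 9.1 says that for acceptability "we will focus on the ease of use and comfortability of the study product, as reported by participants, using information from the Exit Behavioral Survey", and then: "We will present results from the section B of the survey on Gel Acceptability, specifically the following two questions". The items are "B1. Overall how easy or difficult was it to use the gel" and "B2. Overall, how did it feel to have the gel inside you", each with four response levels. The planned outputs are:

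- counts and percentages in each response category, overall and by arm;
- a collapsed favourable proportion for each item, with exact 95% confidence intervals, overall and by arm;
- a Fisher exact test between arms;
- a by-site presentation without testing.

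Two other sections bear on the point. Section 6.1.5 lists "20) behavioral assessment; 21) In-depth interview" among the procedures whose completion is tabulated. Section 2.1 describes a single dose followed by "7 daily doses of the same product to be administered under direct observation in the clinic".

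**The concern.** The endpoint asks a question about content: which features of the gel would make people more or less willing to keep using it. The analysis answers a different and narrower one: how easy and how comfortable the gel was overall, and whether that differed between dapivirine and placebo. A participant who answers *Difficult* has not said what was difficult, or whether it would put them off later use.

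The ratings also describe a short course planned for the clinic: 1 + 7 = 8 doses, with direct observation planned. Section 9.1 does not caution that ease in that setting may differ from ease in unsupervised, sustained use. A report that followed 9.1 to the letter could present favourable percentages for ease and comfort as meeting an objective about sustained use, which neither item measures.

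**Working it through.** The point rests on the text, so the main check sets the objective beside the planned outputs.

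| What section 2.2 asks for | What section 9.1 supplies |
|---|---|
| Attributes of the product | Two broad ones, ease and comfort, each as a single overall rating |
| Whether an attribute hinders or helps | Not asked; direction can be inferred only from the favourable or unfavourable end of the scale |
| Future sustained use | Not asked; both items are in the past tense |
| Findings about dapivirine gel | Active-arm distributions and exact intervals, which do bear on this |
| (Not asked for) | Fisher test of active against placebo |

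**What the Fisher test can show.** It compares ratings between two gels. A difference would suggest that the dapivirine gel is rated differently from the placebo gel. No difference would suggest that they are rated alike, or that the trial is too small to tell. Neither result names a feature that helps or hinders use.

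**How informative the test is, as context only.** The SAP's one power figure (section 2.3.3) is for safety: 85% power for 67% (n = 18) against 11.2% (n = 9) at the 5% level. With a two-sided pooled normal approximation:

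- pooled rate = (18 × 0.67 + 9 × 0.112)/27 = 13.068/27 = 0.484
- null standard error = √[0.484 × 0.516 × (1/18 + 1/9)] = 0.2040
- alternative standard error = √[0.67 × 0.33/18 + 0.112 × 0.888/9] = 0.1528
- z = (0.558 − 1.96 × 0.2040)/0.1528 = 1.035, so power = 0.850

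The stated figure reproduces. Exact two-sided Fisher power for the same rates is 82.5%. The figure concerns safety event rates and says nothing directly about acceptability. The SAP gives no acceptability rates, so the values below are assumptions, shown as a range. Power is the summed binomial probability, at 18 and 9 participants, of all tables with a two-sided Fisher p ≤ 0.05.

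| Assumed favourable, active | Assumed favourable, placebo | Exact Fisher power |
|---|---|---|
| 70% | 90% | 6% |
| 60% | 90% | 22% |
| 50% | 90% | 47% |
| 40% | 90% | 72% |

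**Precision of the descriptive part.** Illustrative Clopper-Pearson 95% intervals, with assumed counts:

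- 22/27 overall: 62% to 94%
- 14/18 active: 52% to 94%
- 7/9 placebo: 40% to 97%

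These intervals are wide but usable as description, and they do not depend on the Fisher test.

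**B2 as written.** B2's four options run from *Very comfortable* to *Very uncomfortable*. The collapsed category is defined by *Liked* and *Liked very much*, which are not among them. The collapsed B2 proportion, its interval and its test therefore cannot be computed as specified. The table of all four categories can.

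**The case against.** The strongest reply is that ease of use and comfort are themselves attributes that can help or hinder use, so 9.1 does bear on the objective. This stands. It also stands that 9.1 plans more than a significance test, since the category distributions and exact intervals are informative without it.

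A second reply is that interview analysis is usually qualitative and is often described in a protocol or behavioural plan. That too stands. Section 9.2 sends mucosal safety to a separate plan and 9.1 contains no such sentence, but the contrast is weak evidence. The exploratory endpoints in section 2.2 also have neither an analysis section nor a deferral in this SAP.

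A reader might infer that the trial cannot answer its acceptability objective, or that the interviews and behavioral assessments will go unused. The document supports neither. It shows only that, within this SAP, those data appear solely in the completion table.

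A third reply is that the full survey is not shown, so attribute or future-use items may not exist. This limits the remedy, which has to be conditional. It does not remove the mismatch, because the endpoint and the analysis are both fixed in this document and differ.

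**Conclusion.** The point holds in a limited form: 9.1 gives partial information on acceptability but does not by itself produce the endpoint stated in 2.2, and the between-arm test does not close the gap. The effect is confined to one secondary endpoint; the primary safety and pharmacokinetic analyses are untouched. The size is qualitative: two broad attributes are covered, future use is not, and no analysis of what helps or hinders use is specified or cross-referenced.

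It would go too far to say that the planned tests will show nothing. The SAP's remark that only very large differences are detectable concerns safety rates, and the acceptability power figures rest on assumed response rates. The conclusion does not depend on them. It assumes only that B1 and B2 are worded in full as shown and that section 9.1 is the whole acceptability analysis in this SAP. The unusable B2 category is a plain error and needs no assumption.

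**What to change.** Amend section 9.1 before the data are unblinded:

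1. Tabulate descriptively, overall and by arm with exact 95% confidence intervals, all product-attribute and future-use items that the Exit Behavioral Survey and the behavioral assessments already contain. Taking all of them avoids choosing items after seeing results. The Clopper-Pearson method in section 5 already covers the binary summaries.
2. Keep B1 and B2 as supportive overall ratings, described as experience under planned directly observed clinic dosing, and label their Fisher tests supportive only.
3. State where the in-depth interviews are analysed for attributes. A cross-reference is enough; this SAP need not prescribe the qualitative method.
4. If the instruments hold no attribute or future-use items, restate the endpoint in section 2.2 as overall ease of use and comfort, so that endpoint and analysis agree.
5. If B2 is kept, define its collapsed category with B2's own response options.

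The cost is SAP wording and a few extra descriptive tables. Step 1 depends on what the instruments contain, which this document does not show; step 4 covers the case where they contain nothing suitable.

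### The collapsed outcome for acceptability question B2 is defined by responses that B2 does not offer, so its proportion, exact intervals and Fisher test have no valid definition as written

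*SAP*

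**What the plan says.** SAP Section 9.1 takes two items from the Exit Behavioral Survey and states the aim as follows: "we will focus on the ease of use and comfortability of the study product". B1 covers ease of use and B2 covers comfort.

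B2 is worded "B2. Overall, how did it feel to have the gel inside you", with four listed answers: "1. Very comfortable", "2. Comfortable", "3. Uncomfortable" and "4. Very uncomfortable".

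The section plans counts and percentages in every category, overall and by arm. For formal testing it collapses each item to a binary outcome. The B1 rule reads "For question B1, we will calculate the proportion of participants that responded “Easy” or “Very easy". The B2 rule reads "For question B2, we will calculate the proportion of participants that responded “Liked” or “Liked very much". The resulting proportions are to be reported with exact 95% confidence intervals, overall and by arm, and compared between arms with Fisher's exact test.

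**The concern.** The B2 rule refers to answers that a participant cannot give on the item as listed. No liking question appears anywhere in the SAP, and nothing says how liking would translate into comfort. The B1 rule, in the sentence before, does use B1's own answers.

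The collapsed outcome is the only input to the B2 proportions, intervals and test. The SAP specifies few between-arm tests: one for the primary safety endpoint (Section 8.1) and one each for B1 and B2 (Section 9.1). The other secondary endpoint, mucosal safety, is deferred to a separate plan (Section 9.2). One of the three specified comparisons therefore has no usable outcome, and it is the only one that addresses comfort. Whoever programs it must supply a definition that the SAP does not contain.

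**Working it through.** **Inputs.** The answers and collapsing rules for B1 and B2 come from SAP Section 9.1. The planned arm sizes, 18 active and 9 control, come from SAP Section 2.3.3. The SAP states no figure for this comparison, so there is none to reproduce.

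**Step 1: match the rule's labels to the listed answers.**

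| Item | Listed answers | Labels in the rule | Labels that match |
|---|---|---|---|
| B1 | Very difficult, Difficult, Easy, Very easy | Easy, Very easy | 2 of 2 |
| B2 | Very comfortable, Comfortable, Uncomfortable, Very uncomfortable | Liked, Liked very much | 0 of 2 |

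**Step 2: apply the B2 rule literally.** No recorded answer can satisfy it, so the favourable count is 0/18 in the active arm and 0/9 in the control arm.

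- Fisher's exact test: with a favourable total of 0, only one 2×2 table has these margins. Its probability is 1, so p = 1. The odds ratio is undefined.
- Clopper-Pearson upper 95% limit for 0/n: 1 − 0.025^(1/n).
  - n = 18: 1 − 0.025^(1/18) = 18.5%
  - n = 9: 1 − 0.025^(1/9) = 33.6%
  - n = 27 (overall): 1 − 0.025^(1/27) = 12.8%

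The zero counts and p = 1 follow at any arm size. The limits depend only on n. None of these results carries information about comfort.

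**Step 3: see what the SAP implies instead.** An ordered scale with four answers has 4 − 1 = 3 possible cut-points. The B1 rule takes the two favourable answers. The same choice for B2 gives *Very comfortable* plus *Comfortable*, which agrees with the section's stated focus on comfort. This is an inference, because the SAP does not state it.

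**Step 4: check what survives.** The four-category table for B2, overall and by arm, does not use the collapsed outcome and stands as planned.

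**The case against.** The best case on the other side is that little harm would follow in practice. B2 is a secondary acceptability item. Its likely meaning is plain from the stated focus and from the B1 rule, so the scope for a data-driven definition is narrow. A reader could rebuild any collapse from the four-category table. With 18 and 9 participants the test can detect only very large differences in any case. Nobody would knowingly report 0/18 versus 0/9, and the realistic outcome is a query and a one-line correction. All of this stands, and it keeps the severity down. It does not supply a definition: an outcome for a formal test should be stated, and here the stated one cannot be used.

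A reader might infer two stronger points that the SAP does not support.

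- *The B2 result would come out reversed.* The favourable answers are numbered 3 and 4 for B1 but 1 and 2 for B2, so a numeric rule carried over from B1 would count discomfort as comfort. The SAP has no numeric rule to carry over, since both items are collapsed by label. A different answer order in two items is not an error. Even if the complement were used in both arms, the two columns of the 2×2 table would merely swap and the two-sided Fisher p-value would be unchanged. Only the reported proportion and its interval would flip.
- *The labels were taken from another survey question.* The survey is not shown and no liking item appears in the SAP, so the source of the wording is unknown. The mistake could lie in the listed question or answers and not in the rule.

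**Conclusion.** The inconsistency is real and lies wholly within SAP Section 9.1: the listed B2 answers and the B2 collapsing rule cannot both be right. As written, the B2 proportion, exact intervals and Fisher test have no valid definition, and the literal result is 0/18 versus 0/9 with p = 1.

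This should be fixed, on a secondary endpoint. The primary endpoints, the B1 analysis and the four-category B2 table are not affected. The mismatch itself needs no assumption beyond the text of the section. The 0/18 and 0/9 denominators assume that every planned participant answers B2. The reading of the intent as *Very comfortable* or *Comfortable* assumes that the listed answers match the survey form.

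**What to change.** 1. Check the wording and answers of B2 in Section 9.1 against the Exit Behavioral Survey.
2. If the listed answers are right, replace the B2 rule with the proportion of participants who answered *Very comfortable* or *Comfortable*. If the survey shows a different question or different answers, correct the listing and write the rule in the survey's own answers.
3. Date the correction before acceptability data are examined by arm. The SAP does not settle how far the trial had progressed. Randomization, enrolment and the safety committee review are described in the past tense, blinding is in the present tense, and unblinding is still to come in Section 3.1. Recording the date shows that the definition did not depend on the results.

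The cost is one sentence in the SAP and one look at the survey form. No additional data, sample size or analysis is needed, and there is no drawback.

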9.2 Mucosal safety

Because the evaluations for safety focused on the rectal mucosal (proteomics, transcriptome, microflora, histology, tissue flow cytometry) include very specialized analyses, these will be described in a separate statistical analysis plan and performed separately.

10. SAFETY ANALYSES

All participants enrolled and administered the study product will be assessed for safety and tolerability.

10.1 Adverse Events and Deaths

See Section 8 for the description of the analyses on Adverse Events as the primary study endpoint related to Safety.

10.2 Laboratory Evaluations Results

10.2.1 Laboratory Evaluations

Laboratory results as collected on the Local Laboratory eCRF will be presented in tables by arm and visit and by site and visit. Summary statistics appropriate for the measurement scale will be used to describe AST (SGOT), ALT (SGPT), and creatinine values and severity grades. No formal statistical testing will be performed.

10.2.1 HIV Testing

Number and percentage of participants with a positive HIV test result as collected on the HIV Test Results eCRF will be presented in tables by arm. No formal statistical testing will be performed.

10.3 Other Safety Measures

10.3.1 Anorectal Exam

Anorectal exam results as collected on the Anorectal Exam eCRF will be presented in tables by arm and visit and by site and visit. Number and percentage of participants with any abnormal perianal examination, digital rectal examination, rectal mucosa from anoscopy, and sigmoidoscopy findings at each visit will be presented as well as the number and proportions of participants with specific findings. No formal statistical testing will be performed.

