7.5 Anorectal and Pelvic Exams

Baseline results from the anorectal exam (all participants) and the pelvic exam (female participants only), as collected on the Anorectal Exam and Pelvic Exam eCRFs at Screening and Enrollment will be presented in tables by arm and visit and by site and visit. Number and percentage of participants experiencing any abnormal findings at each visit will be presented as well as the number and proportions of participants with specific types of anorectal or pelvic exam findings. No formal statistical testing will be performed.

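### Anorectal findings are tabulated only as prevalence at each visit, which cannot separate new from persisting findings, and post-dose pelvic findings have no table of their own

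*SAP*

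**What the plan says.** **Anorectal exam, safety section.** SAP section 10.3.1 sets the layout: "Anorectal exam results as collected on the Anorectal Exam eCRF will be presented in tables by arm and visit and by site and visit". What is counted is given as: "Number and percentage of participants with any abnormal perianal examination, digital rectal examination, rectal mucosa from anoscopy, and sigmoidoscopy findings at each visit will be" shown, together with the number and proportion with each specific finding. It defines no category for new findings, worsened findings or change from the participant's own baseline, and plans no formal test.

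**Baseline exams.** Section 7.5 covers "Baseline results from the anorectal exam (all participants) and the pelvic exam (female participants only"), again as any abnormal finding and as specific findings. The scope is limited in time: "Pelvic Exam eCRFs at Screening and Enrollment will be presented in tables by arm and visit and by site and visit".

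**Pelvic exam elsewhere.** The list of procedures in section 6.1.5 includes "6) pelvic exam *; 7) rectal exam", but that section tabulates whether a procedure was completed, not what it showed. Section 10.3 deals with the anorectal exam and concomitant medications only.

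**Adverse events.** Section 2.2 grades AEs with a general table and the "Female Genital [Dated November 2007], Male Genital [Dated November 2007] and Rectal [Clarification Dated May 2012] Grading Tables for Use in Microbicide Studies". Section 8.1 tabulates AEs by MedDRA term, severity and relatedness for each arm, and adds a listing with onset dates. Section 7.2 lists baseline conditions individually, with dates and ongoing status.

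**The concern.** The gel is applied rectally, so direct examination of the anorectum is an obvious place to look for local effects. The laboratory assessments of the rectal mucosa are deferred by section 9.2 to a separate plan, and visual examination is not among them. In this SAP, section 10.3.1 is therefore the only planned summary of what the anorectal examination itself shows after dosing.

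A count of participants with any abnormality at a visit mixes two groups: those who had the finding before the first dose and still have it, and those who developed it afterwards. Only the second group informs a judgement of local tolerability. The baseline table gives group percentages, not the link between one participant's two exams.

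The pelvic exam raises a simpler point. The plan tabulates pelvic findings before product use and offers no matching table after it, although it studies dapivirine in cervicovaginal fluid and cervical tissue. What is at stake is how well the report can describe low-grade local findings, not the primary comparison.

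**Working it through.** The SAP states no figure on this point, so there is none to reproduce. The check asks what the two planned tables can and cannot identify.

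**Inputs.** Planned arm sizes are 18 dapivirine and 9 placebo (section 2.3.3). The SAP gives no prevalence of anorectal findings, so every count and rate below except the arm sizes is an assumption.

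**1. What two prevalences identify.** Take one arm with *n* participants examined both before the first dose and at a later visit. Let *B* be the number abnormal before, *F* the number abnormal later, *N* those newly abnormal and *R* those whose abnormality resolved. Then

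- *F* − *B* = *N* − *R*
- *N* lies between max(0, *F* − *B*) and min(*F*, *n* − *B*).

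Sections 7.5 and 10.3.1 give *B* and *F*. They fix *N* − *R*, but *N* itself only within these bounds. If nothing resolves (*R* = 0), *N* = *F* − *B* and nothing is lost.

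**2. Width of the bounds.** Assume the prevalence in an arm is the same before and after (*B* = *F*), at roughly 10%, 20% or 30%, rounded to whole participants. The lower bound is 0 and the upper bound is *F*.

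| Assumed prevalence | Dapivirine *B* = *F* | *N* of 18 | Placebo *B* = *F* | *N* of 9 |
|---|---|---|---|---|
| 10% | 2 (18 × 0.10 = 1.8) | 0 to 2 (0% to 11.1%) | 1 (9 × 0.10 = 0.9) | 0 to 1 (0% to 11.1%) |
| 20% | 4 (18 × 0.20 = 3.6) | 0 to 4 (0% to 22.2%) | 2 (9 × 0.20 = 1.8) | 0 to 2 (0% to 22.2%) |
| 30% | 5 (18 × 0.30 = 5.4) | 0 to 5 (0% to 27.8%) | 3 (9 × 0.30 = 2.7) | 0 to 3 (0% to 33.3%) |

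One participant is worth 1/18 = 5.6 points on dapivirine and 1/9 = 11.1 points on placebo.

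**3. How much of a visit's count can be pre-existing.** Suppose a share *b* is abnormal at baseline and stays so, and the others develop a finding with risk *q* = 10%. The share abnormal at the visit is *b* + (1 − *b*)*q*, and the fraction already abnormal at baseline is *b* divided by that.

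- *b* = 5%: 0.05 + 0.95 × 0.10 = 14.5%; 0.05/0.145 = 34%
- *b* = 10%: 0.10 + 0.90 × 0.10 = 19%; 0.10/0.19 = 53%
- *b* = 20%: 0.20 + 0.80 × 0.10 = 28%; 0.20/0.28 = 71%
- *b* = 30%: 0.30 + 0.70 × 0.10 = 37%; 0.30/0.37 = 81%

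So the visit table read alone says little about new findings. Read with section 7.5, it recovers the net change (step 1), but not the new and resolved findings behind it.

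**4. Pelvic findings.** Section 7.5 stops at Enrollment, section 6.1.5 counts completion, and section 10 has no pelvic table. The remaining route is section 8.1, which reaches a pelvic finding only if it was recorded as an AE.

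**The case against.** The case for leaving the plan as it is has weight, and most of it stands.

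- **Attribution to the gel.** A reader might infer that pre-existing lesions are reported as on-product findings. The SAP does not say so. Section 10.3.1 is descriptive, by visit, and does not call the findings new or treatment-emergent. Section 7.5 shows the baseline level in each arm in a matching layout.
- **Masking of an arm difference.** A reader might fear that equal percentages after dosing hide a gel effect, for example 2 of 9 placebo participants with stable findings beside 4 of 18 dapivirine participants with new ones. Both arms would show 22% after dosing, but section 7.5 would show 22% and 0% before it. The rise on dapivirine would be visible. By the bounds above, with *B* = 0 and *F* = 4 all four must be new. What stays open is whether the placebo findings are the same participants' findings (0 to 2 new).
- **Genital findings.** It would be wrong to conclude that new genital findings are not tabulated. Those recorded as AEs appear in the section 8.1 tables, which apart from the primary endpoint have no stated grade floor.
- **Marks from tissue sampling.** One might suppose that these inflate the count. The SAP does not say whether such marks are recorded as abnormal, or whether the exam comes before sampling.
- **Pelvic schedule.** The SAP does not show which visits after dosing include a pelvic exam. That belongs to the protocol, which is not at hand.
- **Status of the table.** It sits under other safety measures, carries no test and feeds none of the endpoints listed in section 2.2.

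None of this supplies the within-participant link between the two exams, or a summary of pelvic findings that are not AEs.

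**Conclusion.** The point holds as a limited one. Sections 7.5 and 10.3.1 together show the prevalence of anorectal findings by arm before and after dosing. They do not show how many participants had a new or worsened finding, because resolution in some can offset appearance in others. With 18 and 9 participants and an assumed stable prevalence of 10% to 30%, the number newly abnormal is undetermined from 0 up to 2 to 5 on dapivirine and from 0 up to 1 to 3 on placebo. These bounds assume that the same participants are examined at both times. The ambiguity vanishes if no finding resolves.

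Separately, if pelvic exams are done after dosing, findings from them that are not recorded as AEs have no planned summary.

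Both gaps concern a supportive descriptive display. Neither touches the primary safety endpoint, its confidence intervals or its test. This is a worthwhile, inexpensive improvement, not an error in the primary analysis.

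**What to change.** In section 10.3.1, define the reference as the participant's last exam before the first dose. Add, by arm and visit and cumulatively after first dose, the number and percentage with a new or worsened finding relative to that exam. A shift table of reference exam against later visit would serve equally well. Keep the planned prevalence table.

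In section 10.3, add the same summary for any post-dose pelvic exams in women. If pelvic findings are meant to be reported only through AEs, an explicit statement would at least remove the doubt, though findings not recorded as AEs would still go unsummarised.

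The anorectal summary uses the same eCRF that sections 7.5 and 10.3.1 already draw on, so it needs SAP wording, a within-participant match and a few more descriptive tables. The pelvic summary depends on which post-dose exams the protocol schedules. Neither change affects the primary endpoint.
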